## **4.8. Pharmacodynamic Data**

### **4.8.1. Variables**

#### **4.8.1.1. MRI**

MRI variables consist of the following:

Variable	Unit	Formula for derivation or SAS variable name/expression from SDTM FA
Total muscle volume (TMV)	mm 	TMV = Contractile muscle tissue volume (SAS variable FASTRESN in SDTM FA where FATESTCD = "MVOL") + Intramuscular fat volume (SAS variable FASTRESN in SDTM FA where FATESTCD="IFATVOL")
Intramuscular fat volume (IMFV)	mm 	SAS variable FASTRESN in SDTM FA where FATESTCD="IFATVOL"
Contractile muscle volume (CMV)	mm 	SAS variable FASTRESN in SDTM FA where FATESTCD="MVOL"
Fat fraction (FF)	%	SAS variable FASTRESN in SDTM FA where FATESTCD="FATF"
Contractile muscle fraction (CMF)	%	CMF = 100 – FF
Calculated contractile muscle volume (CCMV)	mm 	CCMV = TMV * CMF/100
Calculated intramuscular fat volume (CIMFV)	mm 	CIMFV = TMV * FF/100
Contractile muscle mass (CMM)	g	CMM = CMV * 1.06/1000
Intramuscular fat mass (IMFM)	g	IMFM = IMFV * 0.9/1000
Total muscle mass (TMM)	g	TMM = CMM + IMFM
Calculated contractile muscle mass (CCMM)	g	CCMM = CCMV * 1.06/1000
Calculated intramuscular fat mass (CIMFM)	g	CIMFM = CIMFV * 0.9/1000
Calculated total muscle mass (CTMM)	g	CTMM = CCMM + CIMFM

#### 4.8.1.2. Biomarkers

Biomarker data include but are not necessarily limited to the following selected laboratory data: CTX and hemoglobin.

#### 4.8.1.3. CMAP of TA

This is an exploratory variable that is collected for Part 2 patients.

#### 4.8.2. Analyses

##### 4.8.2.1. Part 1

#### MRI

Individual MRI data will be listed.

For each MRI variable, the raw data as well as the absolute and percent change from baseline will be summarized by cohort for each scheduled time and side treated [left and right]. The average absolute and percent change [from left and right sides] will also be provided.

For total muscle volume, calculated contractile muscle volume, fat fraction, and calculated intramuscular fat, least squares estimates of the effect of ACE-083 and corresponding 90% and 95% confidence intervals will be produced for the average percent change data at Day 106 [from left and right sides] (absolute change for fat fraction at Day 106) using an ANCOVA with BASELINE, COHORT, and BASELINE\*COHORT as variables where:

- COHORT represents the dose level of ACE-083 administered to the muscle
- BASELINE represents the baseline value of the parameter of interest
- BASELINE\*COHORT represents the interaction of baseline and cohort

Graphical summaries of the mean  $\pm$  SEM will be provided for each cohort and scheduled time.

Additional analyses may be performed as appropriate.

## **Biomarker Data**

Individual biomarker data will be listed.

Biomarker data will be summarized by cohort and scheduled time for raw data and changes from baseline (absolute and/or percent). Graphical displays will also be provided (e.g. plot of mean  $\pm$  SEM).

### **4.8.2.2. Part 2**

#### **4.8.2.2.1. Double-Blind Period**

##### **MRI: Total Muscle Volume (TMV)**

Individual total muscle volume data will be listed.

Descriptive statistics will be provided by treatment group and scheduled time for raw data and changes from baseline (absolute and percent change) for each side [left and right]. The average absolute change and average of the percent change for the left and right sides will also be provided.

The primary pharmacodynamic analysis will consist of an ANCOVA in order to assess the effect of ACE-083 on the Day 190 average percent change from baseline for the left and right sides. Covariates to be included into the model are TREATMENT, BASELINE, and CMT-TYPE where:

- TREATMENT represents the treatment group (ACE-083 or placebo)
- BASELINE represents the baseline total muscle volume (average of left and right sides)
- CMT-TYPE refers to the type of CMT (e.g. CMT1 or CMTX)

The effect of ACE-083 versus placebo will be estimated using the ANCOVA model described above and tested using a 0.1 significance level (2-sided). The least-square mean estimate along

with the corresponding 90% confidence interval will be provided. In addition, the 95% confidence interval will also be provided.

If the Day 190 TMV has no missing data, then the above ANCOVA model will be used for analysis. If missing data is present, a standard multiple imputation with the above ANCOVA model will be used for analysis as described in [Section 4.11.1](#).

A mixed model repeated measures (MMRM) analysis will be performed to assess the sensitivity to the ANCOVA analysis described above. An unstructured covariance structure will be used to model the within-patient covariance across visits. Other covariance structures will be considered if the unstructured covariance fails. The covariates to be included consist of all of the covariates described above for the ANCOVA with the addition of the following additional covariates: VISIT where VISIT represents the scheduled visit day post first dose of MRI assessment and TREATMENT\*VISIT.

Similar to what was described for the ANCOVA analysis above, if missing data is present, a standard multiple imputation with the above MMRM model will be used for analysis as described in Section 4.11.1.

The statistical analyses described above will be done on the Per Protocol Set and will be considered primary. The analyses described above will also be repeated for the Full Analysis Set.

In addition, a line graph of the mean  $\pm$  SEM of the percent change from baseline will be provided by treatment for each scheduled time.

Additional analyses may be performed as appropriate.

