8. STUDY POPULATION

8.1. Inclusion Criteria

Patients are eligible to be included in the study only if they meet all of the following criteria at screening:

Inclusion Criteria:

- 1. Age ≥ 18 years
- 2. Diagnosis of CMT1 or CMTX confirmed by:
 - a. Clinical presentation and electrodiagnostics
 - b. Genetically confirmed CMT1 or CMTX (Appendix 3) for the patient or first-degree relative
- 3. Part 1:
 - a. Six-minute walk distance (6MWD) of at least 150 meters (without a brace or walker)
 - b. Independent ambulation for at least 10 meters, without a brace
 - c. Left and right ankle plantar flexion MRC grade 4+ to 5, inclusive

Part 2:

- a. $6MWD \ge 150$ and ≤ 500 meters (without a brace or walker); a maximum of 20% of enrolled patients with $6MWD \ge 450$ meters will be included
- b. Left and right ankle plantar flexion MRC grade 4- to 5, inclusive
- 4. Left and right ankle dorsiflexion Medical Research Council (MRC) manual muscle testing (MMT) grade 3 to 4+ inclusive (Appendix 4). No more than 12 of the 40 subjects may have a grade of 3 or 3+ on one or both sides.
- 5. Females of childbearing potential (defined as sexually mature women who have not undergone hysterectomy or bilateral oophorectomy, or are not naturally postmenopausal ≥ 24 consecutive months) must have negative urine pregnancy test prior to enrollment and use highly effective birth control methods (abstinence, oral contraceptives, barrier method with spermicide, or surgical sterilization) during study participation and for 8 weeks following the last dose of ACE-083. Hormonal birth control use must be stable for at least 14 days prior to Day 1. Males must agree to use a condom during any sexual contact with females of childbearing potential while participating in the study and for 8 weeks following the last dose of ACE-083, even if he has undergone a successful vasectomy. Patients must be counseled concerning measures to be used to prevent pregnancy prior to the first dose of ACE-083.
- 6. Ability to adhere to the study visit schedule/procedures, and to understand and comply with protocol requirements
- 7. Signed written informed consent

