The primary pharmacodynamic parameter will be the percent change in total muscle volume (average of left and right side) 3 weeks after the last dose of the double-blind treatment period (Day 190) from the corresponding baseline. A mixed model will be used to assess the treatment effect (ACE-083 vs. placebo) using a 2-sided, 0.10 significance level. If data from the end of treatment visit are missing, the last observation will be carried forward. Additional techniques for handling missing data will also be evaluated as sensitivity analyses to the last observation carried forward approach. Least squares estimates of the effect of ACE-083 and the corresponding 90% confidence interval will be produced. In addition, least squares estimates of the treatment effect and corresponding 90% confidence intervals will be provided for patients having dorsiflexion MRC-MMT grade of 4- to 4+ on both sides.

For each secondary pharmacodynamic parameter, a mixed model will also be used to assess the treatment effect using a 2-sided 0.10 significance level for the following secondary

09 January 2019 Acceleron Pharma Inc. Clinical Study Protocol Study A083-03 Revision: 03

pharmacodynamic variables: percent change from baseline for the average of the left and right side at 3 weeks after the last dose of the double-blind treatment period (Day 190) for intramuscular fat fraction as well as derived variables such as contractile muscle fraction and contractile muscle volume. Least squares estimates of the effect of ACE-083 and corresponding 90% confidence interval will be provided. In addition, least squares estimates of the treatment effect and corresponding 90% confidence intervals will be provided for patients having dorsiflexion MRC-MMT grade of 4- to 4+ on both sides.

For biomarker data (e.g., IGF-1 and CTX) and TA CMAP amplitude, raw data and changes from baseline (percent and absolute change) will be summarized by treatment group and scheduled time. Such analyses will be considered exploratory.

Additional analyses may be performed as appropriate.

Open-label extension

Descriptive statistics for the percent change from baseline will be provided for each pharmacodynamic variable by treatment group for each scheduled time. For pharmacodynamic variables that are measured on the right and left side (i.e., MRI), the descriptive statistics will include summaries for each side and the average of the right and left sides.

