14.3. Determination of Sample Size

There is no formal sample size calculation for Part 1. Six patients in each cohort will provide sufficient data to evaluate safety and preliminary efficacy data.

The sample size calculation for Part 2 is based upon the expected percent change from baseline in total muscle volume of the injected TA 3 weeks after the last dose. A 10% difference between ACE-083-treated and placebo groups in the percent change in total muscle volume from baseline is considered to be clinically meaningful. The SD is estimated to be approximately 10% for each group based on preliminary MRI data for the ACE-083 treated side of the TA muscle from Part 1 of the Phase 2 study in FSHD patients. Assuming a 2-sided type 1 error rate of 0.10, a 10% difference in percent change from baseline between the ACE-083-treated and placebo groups in total muscle volume, a standard deviation of 10% for each group, and a 1:1 randomization, 90% power is achieved with a total sample size of n=36 patients (18 active, 18 placebo), based on a standard t-test. Clinical Study Protocol Study A083-03 Revision: 03 In addition, this sample

In addition, this sample size provides 90% power to detect a 10% difference in 6MWD, based on an assumed estimated SD of 10% (based off of available data from Part 1 of the Phase 2 study in FSHD patients as well as data from Part 1 of this study, 3-weeks post last dose) and a 2-sided type 1 error rate of 0.10.

In order to account for dropouts (up to 10%), 40 patients will be randomized to study treatment (20 active, 20 placebo) to ensure that at least 18 patients per treatment group complete the double-blind treatment period.

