##### 4.7.2.2.1. Double-Blind Period

###### Muscle Strength (MVIC)

Individual MVIC data will be listed.

Descriptive statistics of the raw data as well as the absolute and percent change from baseline will be provided by side treated [left and right]. The average absolute and average percent change from baseline for the left and right sides will also be provided.

A plot of the mean ( $\pm$  SEM) of the average percent change from baseline for the left and right sides by scheduled day and treatment group will also be provided.

An ANCOVA model will be fitted in order to assess the effect of ACE-083 on the average percent change from baseline for the left and right side at Day 190 with the following covariates: TREATMENT, MRC-MMT DECIMAL SCORE, BASELINE, CMT-TYPE where:

- TREATMENT represents the treatment group (ACE-083 or placebo)
- MRC-MMT DECIMAL SCORE represents the conversion of the screening MRC-MMT grade to the decimal version as follows: 5 = 5.0, 5- = 4.67, 4+ = 4.33, 4 = 4.0, 4- = 3.67, 3+ = 3.33, 3 = 3.0, 3- = 2.67, 2+ = 2.33, 2 = 2.0, 2- = 1.67, 1+ = 1.33, 1=1.0
  - This quantity will be the average from the left and right sides and will be computed for each individual patient.
- BASELINE represents the baseline MVIC (average of left and right sides)
- CMT-TYPE refers to the type of CMT (e.g. CMT1 or CMTX)

The effect of ACE-083 versus placebo will be estimated using the ANCOVA model described above and tested using a 0.1 significance level (2-sided). The least-square mean estimate along with the corresponding 90% confidence interval will be provided. In addition, the 95% confidence interval will also be provided. A bar chart of the least squares mean  $\pm$  SEM of the percent change from baseline will be provided.

If the Day 190 MVIC assessment has no missing data, then the above ANCOVA model will be used for analysis. If missing data is present, a standard multiple imputation with the above ANCOVA model will be used for analysis as described in Section 4.11.1.

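### The primary muscle-volume model leaves out screening dorsiflexion grade, which the plan caps, sub-analyses and already uses as a covariate elsewhere: a modest precision and robustness gap, not an error

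*SAP*

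**What the plan says.** **Primary model.** For the Day 190 percent change in TMV (SAP 4.8.2.2.1): "Covariates to be included into the model are TREATMENT, BASELINE, and CMT-TYPE where". The MMRM sensitivity analysis adds only visit and treatment-by-visit. The models for calculated contractile muscle volume, fat fraction and calculated intramuscular fat use the same three terms.

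**Where grade is used.** The MVIC model (SAP 4.7.2.2.1) is fitted "with the following covariates: TREATMENT, MRC-MMT DECIMAL SCORE, BASELINE, CMT-TYPE where". The score is the screening grade converted to decimals and averaged over left and right. The falls model also includes the dorsiflexion decimal score.

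**How the protocol treats grade.** Inclusion criterion 4 (Protocol 8.1) says: "No more than 12 of the 40 subjects may have a grade of 3 or 3+ on one or both sides". For the primary TMV parameter (Protocol 14.2.4), estimates and 90% intervals "will be provided for patients having dorsiflexion MRC-MMT grade of 4- to 4+ on both sides"; Section 14.2.3 makes a similar request for efficacy. This is the only subgroup that Protocol Section 14 singles out.

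**Randomisation.** CMT type is the only stratification factor (Protocol 10.5, SAP 3.2).

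**What remains for grade and TMV.** SAP 4.4.2 tabulates grade at baseline. SAP 4.9 analyses TMV by dorsiflexion grade under two definitions, labels these analyses hypothesis-generating, and drops CMT type from the models. No grade-adjusted TMV estimate in the whole population is planned.

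**The concern.** A factor important enough to be capped at enrolment and given its own subgroup estimate is a natural candidate for adjustment, particularly when it is not a stratum and each arm has only 20 patients. If grade predicts TMV change beyond baseline TMV and CMT type, two things follow. A chance imbalance in weak patients moves the realised treatment difference, and the variance that grade explains stays in the error term. The subgroup analyses can show whether the effect differs by grade, but they do not correct the primary estimate. An adjustment chosen after unblinding would be open to challenge as data-driven.

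**Working it through.** **The plan's own figure (Protocol 14.3).** The inputs are: "Assuming a 2-sided type 1 error rate of 0.10"; a 10-point difference in percent change; and "a standard deviation of 10% for each group, and a 1:1 randomization". With 18 per arm, SE = 10 × √(2/18) = 3.33, and exact two-sample t power is 90.2% (17 per arm gives 88.7%). Allowing for 10% dropout, 36/0.9 = 40. The stated sample size reproduces.

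**Chance of imbalance.** Weak means grade 3 or 3+ on one or both sides. With 12 weak patients among 40, randomised 20:20, the number on active is hypergeometric(40, 12, 20). Probabilities count both directions:

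| Split | Gap in weak proportion | Probability of this or worse |
|---|---|---|
| 8:4 | 0.20 | 30% |
| 9:3 | 0.30 | 8.2% |
| 10:2 | 0.40 | 1.4% |

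Twelve is a ceiling. With 8 weak patients, a gap of 4 or more still has probability 23.5%.

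**Size of the shift.** Let D be the shortfall in TMV percent change in weak patients. The documents give no value, so D is an assumption: central 5, range 2 to 10. If the shortfall applies in both arms, shift = D × (8/20 − 4/20) = 0.20 × D, which is 1.0 point at D = 5, 0.4 at D = 2 and 2.0 at D = 10. Two things reduce it:
- If only treated weak patients respond less, the shift is 5 × (8/20 − 12/40) = 5 × 0.10 = 0.5 point at D = 5.
- If grade correlates 0.5 with baseline TMV (assumed), baseline TMV absorbs about a quarter of it (1 − 0.5² = 0.75 remains).

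**Gain and cost of adjusting.** With 30% weak, grade explains 0.30 × 0.70 × D² = 0.21 × D² of a total variance of 100. One further covariate takes the residual degrees of freedom from 32 to 31 with 36 patients and inflates the variance of the treatment effect by about 1.033. The net variance factor is (1 − 0.0021 × D²) × 1.033. Power with grade uses 18 per arm, averaged over chance splits with 11 weak patients, against 90.2% without it.

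| D | Variance explained | Net variance factor | Power with grade |
|---|---|---|---|
| 0 | 0% | 1.033 | about 89.3% |
| 2 | 0.84% | 1.024 | not computed |
| 5 | 5.25% | 0.979 | about 90.7% |
| 10 | 21% | 0.816 | about 94.6% |

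At D = 0 the interval widens by about 1.5% (√1.033 ≈ 1.016). At D = 5 the net variance gain is about 2%. The break-even is grade explaining about 3% of the variance (1 − 1/1.033), or D of about 3.9.

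**Simulation** (6,000 trials per setting, 18 per arm, 11 weak, baseline TMV in both models, CMT type left out). Over all randomisations, the model without grade is unbiased and its type I error stays between 8.8% and 10.6%. The exposure appears only given a bad split. With 8 or more of the 11 weak patients on active, a true effect of 10, and grade uncorrelated with baseline TMV:
- D = 5: mean estimate 8.6 and power 82% without grade; 10.1 and 87% with it.
- D = 10: mean estimate 6.9 and power 65% without grade; 9.8 and 91% with it.

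A split that extreme in that direction occurs in roughly 7% of trials (half of 14.6%).

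**The case against.** The strongest case for leaving the model alone has several parts.

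- **Grade is not stated to be prognostic.** A reader might infer from the cap and the subgroup that the protocol regards grade as driving TMV response. It gives no rationale for the cap and never says so. Use of a strength scale for MVIC and falls does not show that it predicts MRI volume change. This stands.
- **Covariates are endpoint-specific.** The walk tests use height; Berg, CMT-HI and CMTES2 use their own baseline and CMT type. The protocol names no covariates for the primary model, so the SAP contradicts nothing. This stands: the omission is a choice without a stated reason, not an inconsistency.
- **The estimate is valid.** A reader might infer bias or an inflated error rate. Over randomisation there is neither. This stands for the comparison as randomised. The SAP makes the Per Protocol Set primary (4.2), where exclusions after randomisation weaken the argument somewhat.
- **The shift is small.** One point is about 0.3 of the SE of 3.33, the 30% counts both directions, and it assumes the full 12 weak patients. This stands and limits the weight of the point.
- **The covariate is not the factor used in the calculation.** A 3+/4+ patient counts as weak but averages (3.33 + 4.33)/2 = 3.83, above a 4-/4- patient at 3.67, who does not. The decimal score would therefore correct such an imbalance only approximately.
- **Checks exist.** Baseline tables would show an imbalance, and the subgroups bear on it. Neither yields an adjusted estimate in the whole population, so this does not close the gap.

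**Conclusion.** The point holds as a precision and robustness gap in the primary TMV model, its MMRM and the other MRI models. At the cap of 12 weak patients there is a 30% chance of an 8:4 or worse split. An 8:4 split shifts the estimate by up to about 1.0 point (0.4 to 2.0) of the 10-point target, less if baseline TMV absorbs part of it or only treated patients differ. All of this rests on an assumed 5-point shortfall (range 2 to 10) that the documents do not supply.

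The efficiency case is modest: about 2% less variance at 5 points, and a small loss at 2 points. A reader who assumes that grade explains 10% of variance would arrive at about 7% (0.90 × 1.033 = 0.93), but that needs D of about 6.9. If grade only modifies the response to drug, there is roughly no gain in power. The case for adjusting is mainly protection against an unlucky split, using a baseline value already collected. It does not show that the estimate is biased or that the sample size is wrong.

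**What to change.** Before unblinding, add the screening dorsiflexion MRC-MMT decimal score (average of left and right, as defined for MVIC) to the ANCOVA and MMRM models for TMV, calculated contractile muscle volume, fat fraction and calculated intramuscular fat in SAP 4.8.2.2.1. If the sponsor prefers to keep the primary model as it is, the minimum is to pre-specify a grade-adjusted TMV sensitivity analysis in the whole analysis population, not only within subgroups.

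The cost is a line of SAP text per model and one degree of freedom. If grade proves unrelated to TMV change, the interval widens by about 1.5% and power falls by about 1 point (90.2% to about 89.3%). No new data and no change in sample size are needed.

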### **MRI: Calculated Contractile Muscle Volume (CCMV), Fat Fraction (FF), and Calculated Intramuscular Fat (CIMV)**

Individual data will be listed.

Descriptive statistics will be provided by treatment group and scheduled time for raw data and changes from baseline (absolute and percent change) for each side [left and right]. The average absolute and average of the percent change for the left and right sides will also be provided.

An ANCOVA model will be fitted in order to assess the effect of ACE-083 on the Day 190 average of left and right side percent change (absolute change for FF) from baseline. Covariates to be included in the model are TREATMENT, BASELINE, and CMT-TYPE where:

- TREATMENT represents the treatment group (ACE-083 or placebo)
- BASELINE represents the baseline parameter of interest (average of left and right sides)
- CMT-TYPE refers to the type of CMT (e.g. CMT1 or CMTX)

For each of the selected MRI parameters, the effect of ACE-083 on the Day 190 average percent change (absolute change for FF) from baseline will be estimated using the ANCOVA model described above and tested using a 0.1 significance level (2-sided). The least-square mean estimate along with the corresponding 90% confidence interval will be provided. In addition, the

95% confidence interval will also be provided as well as a bar chart of the least squares mean estimates ( $\pm$  SEM) for each of the treatment groups.

If the Day 190 selected MRI parameter has no missing data, then the above ANCOVA model will be used for analysis. If missing data is present, a standard multiple imputation with the above ANCOVA model will be used for analysis as described in [Section 4.11.1](#).

A mixed model repeated measures (MMRM) analysis will be performed to assess the sensitivity to the ANCOVA analysis described above. An unstructured covariance structure will be used to model the within-patient covariance across visits. Other covariance structures will be considered if the unstructured covariance fails. The covariates to be included consist of all of the covariates described above for the ANCOVA with the addition of the following additional covariates: VISIT where VISIT represents the scheduled visit day post first dose of MRI assessment and TREATMENT\*VISIT.

Similar to what was described for the ANCOVA analysis above, if missing data is present, a standard multiple imputation with the above MMRM model will be used for analysis as described in [Section 4.11.1](#).

The statistical analyses described above will be done on the Per Protocol Set and will be considered primary. The analyses described above will also be repeated for the Full Analysis Set.

In addition, a line graph of the mean  $\pm$  SEM of the percent change from baseline will be provided by treatment for each scheduled time. For fat fraction, the line graph to be generated will consist of the mean  $\pm$  SEM of the absolute change from baseline by treatment for each scheduled time.

Additional analyses may be performed as appropriate.

